Data Analysis. Our primary study outcomes are to compare change in knowledge pre and post visit (through MMIC knowledge questions), patient satisfaction with GC visit after completion (GCSS) and genetic counseling visit completion rate between IPGC and TGC. Secondary objectives include comparison of empowerment score (GCOS), informed choice (MMIC scale), genetic testing completion, and cancelation/failure rates between the arms.

To evaluate intervention effects, we will conduct univariable and multivariable analysis for comparisons of each outcome of interest between intervention (TGC) and control group (IPGC). For the survey data, we will examine the data from each survey as well as total score or overall index of multiple questionnaires and compare them between the two study arms. We will perform linear regression models for continuous outcomes (e.g., total score of questionnaires) and logistic regression models for binary outcomes that are based on binary response (e.g., visit completion rates, test cancelation/failure and test completion rates). To compare binary outcomes between arms (such as visit completion rate), we will test by comparing rates of each arm via Chi-squared analysis and control for potential confounders. Potential covariates under consideration (e.g., age, race, sex, language, etc.) will be assessed as necessary and adjusted in multivariable models accordingly. We will evaluate whether there is any evidence of multi-collinearity issues among these variables to be adjusted in the model. Possible effect modifiers of intervention effects will be also evaluated by testing interactions (e.g., sex) and addressed to develop the final multivariable models, as well as reporting the intervention effect stratified as an effect modifier. Underlying assumptions of aforementioned regression models including linearity of associations will be also evaluated. We will examine dropouts or missing data to be able to identify accurate missing data mechanisms and select the best statistical approach. All analyses will be performed using SAS 9.4 (SAS Institute Inc, Cary, NC) at a statistical significance level of  $p=0.05$ .

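### No primary model is named and interaction tests on the trial data shape the final one, so the plan permits the reported treatment effect to be chosen after the data are seen

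*Combined protocol and SAP*

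**What the plan says.** The Data Analysis paragraph in section 4.a of the combined protocol and SAP is the only place that sets out the models.

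- **Analyses per outcome.** To evaluate the intervention, "we will conduct univariable and multivariable analysis for comparisons of each outcome of interest". Continuous outcomes get linear regression and binary outcomes get logistic regression.
- **Binary outcomes, including visit completion.** The paragraph adds: "we will test by comparing rates of each arm via Chi-squared analysis and control for potential confounders".
- **Covariates.** "Potential covariates under consideration (e.g., age, race, sex, language, etc.) will be assessed as necessary and adjusted in multivariable models accordingly".
- **Effect modifiers.** Interactions with arm are tested on the trial data, with sex as the only example given, and these are "addressed to develop the final multivariable models". The treatment effect is also to be reported within strata of a modifier.
- **Level.** All analyses use 0.05.

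There are three primary outcomes: change in knowledge, satisfaction (GCSS) and visit completion. Table 1 lists instruments, outcome measures and detectable differences, but no model and no covariates. No section says which analysis gives the primary result, closes the covariate list, lists the interactions, or labels the interaction and stratified results as exploratory.

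**The concern.** In a randomised comparison the primary estimate should come from one analysis fixed in advance. Here each primary outcome can yield an unadjusted result, an adjusted result from an open covariate list, a result from a model containing whichever interactions proved significant, and effects within strata. All are judged at 0.05 and none has priority. If any of them may carry the conclusion, the error rate for that conclusion exceeds 5%.

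The choice also changes what is estimated. Adjusted and unadjusted odds ratios are different quantities even under perfect randomisation. Once an interaction enters a model, the meaning of the arm term depends on how the modifier is coded.

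The stake differs by outcome. Section 1 predicts significantly higher visit completion with telephone counseling, so a false positive there would support the hypothesis. For knowledge and satisfaction it predicts no significant difference, so the open choice could also favour a non-significant result. The false-positive figures below do not measure that second risk.

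**Working it through.** **1. Which analysis do the plan's own power figures describe?** Inputs are from the sample-size paragraph of section 4.a and Table 1: 100 per arm, 80% power, two-sided 0.05.

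- Continuous: n per arm = 2(1.960 + 0.842)² / 0.398² = 15.70 / 0.1584 = 99.1, so 100. A two-sample t-test with 100 per arm has a detectable difference of 0.3981 SD. The stated 0.398 SD is reproduced.
- Visit completion, 63% against 81.6%: the two-proportion formula gives 90 per arm, or 101 with continuity correction. The stated figure is reproduced to within a patient or so.

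Both are simple two-group comparisons. They do not describe a multivariable model built from the data.

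**2. What does the open choice do to the error rate for a continuous outcome?** Simulation with no treatment effect, 100 per arm, linear regression, 4,000 trials per setting. Assumed, because the documents do not say: four independent covariates (age, sex, language, race) that together explain R² = 0, 0.1 or 0.3 of outcome variance; interactions tested at 0.05 for sex, language and race; effects in both strata reported when an interaction is significant.

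| What counts as a claim | R² = 0 | R² = 0.1 | R² = 0.3 |
|---|---|---|---|
| Unadjusted comparison only | 5.2% | 5.2% | 4.8% |
| One fixed model, arm plus all four covariates | 5.2% | 5.0% | 4.8% |
| One model, covariates screened on outcome alone (p<0.2) | 5.0% | 5.0% | 4.8% |
| Either the unadjusted or the fully adjusted result | 5.8% | 6.6% | 7.3% |
| Most favourable of all 16 covariate subsets | 6.2% | 9.0% | 12.2% |
| Screened model, plus strata when an interaction is significant | 13.8% | 12.5% | 11.3% |
| The same, plus the unadjusted result | 14.1% | 13.9% | 13.4% |

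The simulation standard error is √(0.05 × 0.95 / 4000) = 0.3 percentage points near 5% and √(0.13 × 0.87 / 4000) = 0.5 points near 13%.

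The first three rows hold the nominal level. Inflation appears when more than one result may count, and most of it comes from the triggered strata. With three independent interaction tests, at least one is falsely significant with probability 1 − 0.95³ = 14.3%. The row for 16 subsets is a deliberate search that the plan does not describe. It only marks how far an open covariate list could be pushed.

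**3. Is visit completion different?** The same kind of null simulation, with 100 per arm, about 63% completing, four covariates from none to strongly prognostic and three interactions, gave 5.9-7.5% for either chi-squared or adjusted logistic. It gave about 14% once triggered strata count. A second set of runs gave 5.6-7.1% for the better of the two tests. Each single fixed test stayed at about 5%.

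**The case against.** The strongest reply is that the paragraph describes ordinary practice and nothing in it says the most favourable result will be reported. That stands. A reader might infer that the reported effect will be selected after the fact; the text only leaves this open.

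Four other stronger readings are tempting, and the documents do not support them.

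- *Testing covariates raises the error rate.* Screening on the outcome alone and reporting that one model holds 5% (third row of the table). Adjustment is not the fault.
- *A chi-squared test cannot control for confounders, so visit completion has no coherent test.* The sentence "via Chi-squared analysis and control for potential confounders" is loose, but a stratified chi-squared test does adjust, and the preceding sentence assigns binary outcomes to logistic regression. A fair reading is chi-squared unadjusted and logistic adjusted. What remains is that neither is primary.
- *False interactions are nearly certain to intrude.* Four interactions for each of three outcomes would give 1 − 0.95¹² = 46% for at least one. The plan names only sex as an example, the outcomes come from the same patients, and a false interaction is not a false treatment claim.
- *An interaction turns the arm term into a subgroup effect with a larger standard error.* That is true under reference coding; centring the modifier avoids it. No coding is stated, and the plan says stratified effects will be reported as such.

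It can also be said that this is a pilot, and that two of the three primary hypotheses expect no difference. Both facts narrow the consequence. But the study names primary outcomes, gives detectable differences at 80% power and tests at 0.05, and visit completion is expected to differ significantly. For that outcome above all, the primary test needs a name.

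**Conclusion.** The concern holds in a limited form. Section 4.a states a rule under which interaction tests on the trial data shape the final models and stratified effects are reported, beside unadjusted and adjusted results at the same level. No other section names a primary one. The plan therefore permits choice of the reported effect after the data are seen.

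The chance of a false claim per outcome is about 6-7% if either the unadjusted or the adjusted result counts, and about 11-14% if interaction-triggered strata also count, against 5% for one fixed model. These sizes rest on four assumed covariates, three assumed interactions and a reader who accepts any significant result as a claim. Other counts or strengths would move them. The direction does not depend on those choices. The point should be settled before analysis, but it does not threaten the design.

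**What to change.** Before data are examined, replace the model-building sentences in section 4.a with one named primary analysis per primary outcome:

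- **Knowledge:** linear regression on arm and pre-visit score, plus a short fixed list such as site, language and age.
- **Satisfaction:** linear regression on arm plus the same list.
- **Visit completion:** one named test. This can be logistic regression with the same list, reported as a standardised risk difference, or the unadjusted two-group comparison that the power calculation uses.

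Make the other comparison a sensitivity analysis. List the few interactions of interest, for example language and sex, as exploratory, and state that they never enter the primary model. The covariates above are an example; what matters is that the list is closed in advance.

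The cost is a paragraph of text. Age, language and sex are on the list of recorded data, the pre-visit survey supplies the knowledge score, and site should be recoverable from where the patient was scheduled. The sample size does not change, and one fixed adjusted model held the error rate at 4.8-5.2% in the simulation. The small downside is losing the freedom to choose covariates later.

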## Form A

IRB #	STU -----
-------	-----------

SC will attempt to contact patients who cannot be reached the following business day.

Patients who do not complete pre-appointment survey will be excluded from study but will continue with scheduled genetic counseling appointment as standard of care.

Pre-appointment survey completion status and survey completion method will be recorded in RedCap by SC.

Genetic Counseling and Genetic Testing. Patients who are unable to watch the educational video prior to, or during their genetic counseling visit will be excluded from the study. They will still continue with their appointment, but not through the study. Patients excluded for this reason will be recorded in RedCap by SC.

Sample failure and test completion status will be recorded in RedCap by SC. Failure to complete testing will not exclude patient from the study itself.

Post-Appointment Survey and Study Incentive. SC will send post-appointment survey within 24 hours of GC appointment. A Spanish version of the survey will be sent to Spanish-speaking patients.

The post-appointment survey will consist of the Multi-dimensional Model of Informed Choice (MMIC) assessment, the Genetics Outcome Scale (GOS) and the Genetic Counseling Satisfaction Scale (GCSS).

SC will monitor survey completion status. Those with incomplete post-appointment surveys will receive reminder two business days post-appointment and will be offered option to complete the survey via telephone with SC.

If patient is not reached, SC will attempt to contact patient the following day (three business days post-appointment).

Those with incomplete surveys one week after the genetic counseling appointment will be excluded from study. This data will be recorded in RedCap.

Those who complete study surveys will be sent a \$15 gift card electronically.

Location/Setting. For IPGC, patients will be seen within PHHS/JPS clinics. Spanish translation services are provided through PHHS and JPS for patients in their institutions. TGC patients will not be required to be in a certain environment, but we anticipate they will be in their homes or workplace in a secure, private location. GCs will either be in a HIPPA compliant setting offsite or within a UTSW workspace for TGC visits.

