We anticipate a post-enrollment dropout (failure to complete the surveys) rate of 30% given our work with the underserved population. We plan to enroll 280 patients at a 1:1 ratio per arm (100 individuals enrolled per arm), expecting 200 to complete measured responses. We will monitor the dropout rate after the initial 50 individual responses are completed and adjust accrual for study-specific dropout until we have 200 participants' complete measured responses. With 200 patients we will enroll, we can detect mean differences of 0.398 standard deviation (SD) between two study arms with 80% power at a significance level of 0.05 (Table 1). For example, assuming SD of 2 for the GCSS, we will be able to detect a minimum difference of 0.8 ( $=0.398*2$ ) between two study arms with 100 participants enrolled per arm. For GCOS, assuming SD of 46.58, we will be able to detect a minimum difference of 18.54 between pre- and post-visit scores. For visit completion as the primary binary outcome variable, we will be able to detect a minimum difference of 18.6% assuming 63% in the control group, e.g., 81.6% (intervention) vs. 63% (control) with 80% power at significance level of 0.05. Of note, previously published outcomes and unpublished internal data will serve as a baseline for the study population.

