**Form A**

IRB #	STU -----
-------	-----------

*Table 1.* Summary of instrumentation with objectives, measures and distribution plan. Summary of data analysis plan per primary and secondary objectives. Minimum detectable difference between two study arms with 80% power at 2-sided significant level of 0.05 (n=100 per arm)

Aims	Objective Type	Instrumentation	Outcome Measure	Distribution	Minimum Detectable Effect Size at 80% power
Aim 1: Patient Satisfaction	Primary	GCSS	Whole scale score	Post	+/-0.8 points, assuming SD = 2 
Aim 1: Knowledge	Primary	MMIC (8 knowledge questions)	Measure score difference from pre/post	Pre and Post	+/-2 points, assuming SD = 5.03
Aim 1: Informed Decision Making	Second	MMIC (entire measure)	Measure score difference from pre/post	Pre and Post	n/a
Aim 1: GC-specific empowerment	Second	GOS	Measure score difference pre/post	Pre and Post	+/-18.54 points, assuming SD = 46.58 
Aim 2: GC visit completion	Primary	Database query	Proportion of visits scheduled and completed	n/a	18.6%, assuming 63% in control group 
Aim 2: Genetic test completion	Second	Database query	Proportion of genetic tests completed w/n 60d of visit	n/a	19.4%, assuming 77.4% in control group 
Aim 2: Genetic test cancellation/failure	Second	Database query	Proportion of genetic tests initiated compared to tests canceled/failure	n/a	15%, assuming 9% in control group 

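### The plan excludes survey non-completers yet leaves the missing-data method to be chosen from the data: the two rules conflict, and the likely result is a completers-only comparison with about 30% lost

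*Combined protocol and SAP*

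**What the plan says.** All the relevant text is in Form A, item 4.a.

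- **Before the visit:** "Patients who do not complete pre-appointment survey will be excluded from study". This step follows randomization and verbal consent.
- **After the visit** (Post-Appointment Survey and Study Incentive): "Those with incomplete surveys one week after the genetic counseling appointment will be excluded from study".
- **Data Analysis:** the plan is to examine dropouts or missing data so as to "identify accurate missing data mechanisms and select the best statistical approach". No method, assumption, analysis population or sensitivity analysis follows.
- **Sample size:** "We anticipate a post-enrollment dropout (failure to complete the surveys) rate of 30" percent. The text goes on: "We plan to enroll 280 patients at a 1:1 ratio per arm (100 individuals enrolled per arm), expecting 200 to complete measured responses". After the first 50 responses the sponsor will "adjust accrual for study-specific dropout until we have 200" complete responders are in hand.
- **Table 1** gives the "Minimum detectable difference between two study arms with 80% power at 2-sided significant level of 0.05 (n=100 per arm"). I read 100 per arm as the completer count, since 280 enrolled at 1:1 is 140 per arm.

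The covariates named for the multivariable models are examples (age, race, sex, language) to be adjusted for as necessary. Neither the pre-visit score nor site is named.

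**The concern.** There are three linked problems.

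1. **The rules conflict.** A missing-data method works on patients who stay in the analysis with an outcome missing. If those patients have been excluded from the study, the method has nothing to act on.

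2. **The planned step cannot be done.** Observed data can give evidence against missing completely at random. They cannot distinguish missing at random from missing not at random, because that difference lies in the unseen values. Choosing a method after looking at the data also leaves the primary result open to choice.

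3. **The randomized comparison is not protected.** Increasing enrolment to allow for dropout preserves power but does not keep the arms comparable. Bias arises if the arms lose different shares of patients, or different kinds of patients. The trial's own hypothesis is that telephone counseling (TGC) raises visit completion over in-person counseling (IPGC), so unequal loss is plausible. It also expects no significant difference in knowledge or satisfaction, so bias could hide a true deficit as easily as create a false one.

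**Working it through.** **Reproducing the plan's figures.** With 100 completers per arm, a two-sided 5% level and 80% power, the two-sample t-test detects 0.3981 SD. The plan says "we can detect mean differences of 0.398 standard deviation (SD) between two study arms with 80% power at a significance level of 0.05", which agrees. On enrolment, 200/(1 − 0.30) = 286 against 280 stated, and 280 × 0.70 = 196 against 200 stated. Going from 280 to 200 is a loss of 80/280 = 28.6%. So a loss of about 30% is the plan's own figure, and enrolment already allows for it.

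**Bias formula.** Let f be the share lost in an arm, and g the completer mean minus the lost-patient mean, in SD. Completers then overstate the mean of the whole retained arm by f × g. The bias in TGC minus IPGC is

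bias = f_T × g_T − f_C × g_C.

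The plan gives an overall loss of 30%, no split by arm, and no value of g. Every g below is an assumption.

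**Equal loss, 30% in each arm** (140 enrolled and 98 completers per arm):

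- Same g in both arms: bias = 0 and type I error = 5%.
- g = 0.5 SD in one arm only: bias = 0.30 × 0.5 = 0.15 SD, which is 38% of 0.398 SD. Type I error is about 18%.

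**Unequal loss, one illustrative scenario.** The sample-size example for visit completion is 63% (IPGC) against 81.6% (TGC), so non-attendance is 37% and 18.4%. Assume that survey loss equals non-attendance, that all attenders respond, and that g is the same in both arms. Then |bias| = g × (0.37 − 0.184) = 0.186 × g. With 100 completers per arm the standard error is √(2/100) SD, so the noncentrality is |bias| × √50. Type I error is 1 − Φ(1.96 − nc) + Φ(−1.96 − nc).

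| Assumed g (SD) | Bias (SD) | Share of 0.398 SD | Noncentrality | Type I error |
|---|---|---|---|---|
| 0.3 | 0.056 | 14% | 0.39 | 6.8% |
| 0.5 | 0.093 | 23% | 0.66 | 10.1% |
| 0.8 | 0.149 | 37% | 1.05 | 18.3% |

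Using the completer counts that follow from 140 enrolled per arm (140 × 0.63 ≈ 88 and 140 × 0.816 ≈ 114) changes little: the standard error is √(1/88 + 1/114) ≈ 0.142, against 0.141 above. If lost patients would have scored lower, the bias runs against TGC. If they would have scored higher, it favors TGC.

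**The case against.** **A completers-only analysis is inferred.** A reader might conclude that the protocol specifies one. It does not. No analysis set is named, exclusions and their reasons go into REDCap, and the Data Analysis paragraph leaves room for another method. Exclusion might even be meant operationally. This stands as a limit on the claim. But non-completers are said to leave the study, and both accrual and power count completers, so it remains the natural reading. If it is wrong, the text still has to be reconciled.

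**The 37% and 18.4% are not forecasts of survey loss.** A reader might take them as the plan's expected dropout by arm. The 81.6% is only an example of a detectable difference. The protocol expects higher completion under TGC without giving a size, and it does not say whether a no-show counts as a survey dropout. The survey cohort (reached by telephone, consented, pre-visit survey done) is also narrower than all scheduled visits. The table above is therefore one scenario, and the zero-bias case belongs beside it.

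**Imputation adds little.** When only the post-visit score is missing, completer regression adjusted for the baseline predictors is valid under missing at random given those predictors. Imputing from the same variables gains little. This is correct, and the fix accepts either method. It does not excuse leaving the method open, and neither method handles lost patients who still differ after adjustment.

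**Scope.** Visit completion comes from a database query and needs no survey response, and the study is described as a pilot. Both are true. Knowledge and satisfaction are still primary outcomes that depend on surveys.

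**Conclusion.** The concern holds in this form: the exclusion rules and the missing-data sentence conflict, the mechanism cannot be identified as planned, and no primary method or sensitivity analysis is fixed, although about 30% of survey outcomes are expected to be lost. The issue is bias in two of the three primary outcomes. A reader might also infer a shortfall in power, but the documents do not support that, because accrual continues to 200 completers.

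The size cannot be determined from the documents. It runs from zero (equal loss and equal selection) to 0.06–0.15 SD, with type I error of 7% to 18%, in the illustrative unequal-loss scenario. That range assumes survey loss equal to non-attendance at 37% and 18.4%, and a gap of 0.3 to 0.8 SD common to both arms. Equal 30% loss with a 0.5 SD gap in one arm only also gives 0.15 SD. This should be corrected before analysis.

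**What to change.** 1. **Status.** Where the post-visit survey is incomplete, record it as a missing post-visit survey in place of exclusion from the study. Keep every consented patient with a pre-visit survey in the assigned arm. No-shows then also stay in the visit-completion denominator. State whether the exclusion for not watching the video, which can fall after the pre-visit survey, still removes a patient from analysis.

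2. **Primary method.** Replace the sentence on identifying mechanisms with a pre-specified analysis under missing at random. For knowledge and empowerment, regress the post-visit score on arm, pre-visit score, age, sex, language and site, or use multiple imputation by arm from the same variables. Site is not in the list of recorded fields but should be derivable, since patients are scheduled at two named hospitals. Analyse satisfaction among attenders, because it has no meaning without a visit.

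3. **Target population.** State whether the knowledge comparison covers attenders only or all retained patients and, if the latter, what a no-show's post-visit value represents. Imputing it from completers supplies a value as if the visit had taken place, which answers a different question from the attender-only satisfaction analysis.

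4. **Sensitivity.** Add a delta-shift analysis, varied separately by arm. Use surveys returned after one week only in a flagged sensitivity analysis, because they change the timing of measurement.

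**Cost.** A protocol and SAP wording change and a little more analysis. The main analysis will rest on missing at random. Patients excluded before completing the pre-visit survey (not reached, declined, chose the other delivery model, or left that survey incomplete) are not recovered, so total loss from randomization will still exceed the survey dropout figure.

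### The sample-size paragraph gives two enrolment sizes (280 and 200) and ties the detectable differences to enrolled patients instead of completers; visit completion borrows the completer N

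*Combined protocol and SAP*

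**What the plan says.** Section 4.a, Data Analysis, sample-size paragraph:

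- Dropout: "We anticipate a post-enrollment dropout (failure to complete the surveys) rate of 30" percent.
- Enrolment: "We plan to enroll 280 patients at a 1:1 ratio per arm (100 individuals enrolled per arm), expecting 200 to complete measured responses".
- Accrual: after the first 50 completed responses the team will "adjust accrual for study-specific dropout until we have 200" participants with complete responses.
- Power for means: "With 200 patients we will enroll, we can detect mean differences of 0.398 standard deviation (SD") at 80% power and a 0.05 significance level. The GCSS example (SD 2, difference 0.8) is stated "between two study arms with 100 participants enrolled per arm".
- Visit completion: 18.6 points, 63% (control) against 81.6% (intervention). The sentence gives no N.

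Table 1 has one caption for all rows: "Minimum detectable difference between two study arms with 80% power at 2-sided significant level of 0.05 (n=100 per arm"). Its visit-completion row defines the measure as "Proportion of visits scheduled and completed".

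Two procedural sections also matter. Under Randomization and Scheduling, patients are randomised from the referral queue and then scheduled; the eligibility call and consent come later, one week before the appointment. Under Post-Appointment Survey and Study Incentive, the post-visit survey goes out within 24 hours of the appointment, and "Those with incomplete surveys one week after the genetic counseling appointment will be excluded from study".

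**The concern.** Planned enrolment is a core protocol figure, and here one sentence supports two values 80 patients apart (280 − 200). The per-arm figure also has a practical use, because the coordinator is told to watch the numbers per arm and adjust recruitment. The main power statement then names the wrong population: it speaks of enrolled patients, while its figure holds for patients with complete data.

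Visit completion is one of the three primary outcomes. A caption N that matches the survey completers does not fit an outcome that counts how many scheduled patients attended. In a set selected for having returned a post-visit survey, attendance would be essentially 100% in both arms, not 63% in one of them. Unless the denominator is named, a reader cannot tell what the 18.6 points refers to, and an analyst who applied the exclusion rules literally could not estimate the outcome.

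**Working it through.** **Inputs.** From the sample-size paragraph and Table 1: two-sided 0.05, 80% power, 100 per arm, 280 enrolled, 30% dropout, 200 completers, GCSS SD 2, visit completion 63% against 81.6%.

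**1. Enrolment.**
- 280 / 2 = 140 per arm; 2 × 100 = 200.
- 280 × 0.7 = 196, close to the 200 expected to complete. In reverse, 200 / 0.7 = 285.7, about 2% above 280.
- 200 × 0.7 = 140, which is not 200. So 280 fits as the enrolled number and 200 as the completers; 200 cannot be both.

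**2. The plan's difference in means.** Two-sample t-test, n per arm; the normal approximation is (1.96 + 0.842) × √(2/n).
- n = 100: 0.396 SD by the approximation and 0.398 SD by the noncentral t, with 80.0% power. This reproduces the plan. GCSS: 0.398 × 2 = 0.80.
- n = 98 (196 completers): 0.402 SD; power at 0.398 SD is 79.2%.

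The stated figure therefore belongs to 100 *analysed* participants per arm.

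**3. The plan's difference in visit completion.** With p̄ the mean of the two proportions and c = 0 (uncorrected) or 1 (continuity-corrected),

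power = Φ{ [Δ − c/n − 1.96 √(2p̄(1−p̄)/n)] / √([p₁(1−p₁) + p₂(1−p₂)]/n) }.

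For 0.63 against 0.816 and n = 100, p̄ = 0.723:
- 1.96 × √(2 × 0.723 × 0.277 / 100) = 0.124
- √((0.2331 + 0.1501)/100) = 0.0619
- corrected: (0.186 − 0.010 − 0.124)/0.0619 = 0.84, power 80%
- uncorrected: (0.186 − 0.124)/0.0619 = 1.00, power 84%

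Solving for 80% power gives 18.61 points corrected and 17.71 uncorrected. The plan's 18.6 is the continuity-corrected value at 100 per arm.

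**4. Can 100 per arm be the visit-completion denominator?** A participant with complete responses has returned a post-visit survey and so has attended. At the plan's 63% control attendance, 100 attenders need at least 100 / 0.63 = 158.7, that is 159 scheduled. This is a lower bound, because some attenders will have declined, been excluded or not returned a survey.

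**5. Detectable difference at a plausible N.** The documents give no number scheduled, so these N are assumptions (equal arms, 63% in control, 80% power):

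| Scheduled per arm (assumed) | Uncorrected | Continuity-corrected |
|---|---|---|
| 159 | 14.3 points | 14.9 points |
| 200 | 12.9 points | 13.3 points |

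The enrolled number, 140 per arm, is not a usable stand-in: 140 × 0.63 = 88 attenders in the control arm, fewer than the 100 completers required.

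**The case against.** The strongest reply is that the paragraph resolves itself. Dropout of 30%, 280 enrolled, 200 completing and accrual until 200 complete admit only one reading, so what remains is the word for enrolment used loosely three times. That stands as far as power is concerned, and it limits the point to a wrong stated size and label. It does not remove the contradiction, since both totals are described as enrolled.

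A reader might infer that the trial is underpowered. If only 200 were enrolled and 30% dropped out, 70 per arm would remain, giving a detectable difference of 0.477 SD and 64.7% power at 0.398 SD. The documents do not support this, because the accrual rule continues until 200 have complete responses.

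On visit completion, it can fairly be said that Table 1 does give an N in its caption and that 18.6 points reproduces with it. So it would be wrong to say that no N is given. What is missing is the expected number *scheduled*. It is also true that any mismatch is in the safe direction: every completer was first scheduled, so the scheduled set cannot be smaller than 100 per arm.

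Finally, 280 is about 2% short of the exact inflation to 286. The dropout monitoring already covers that gap, and no second enrolment figure is needed.

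**Conclusion.** The stated enrolment is wrong as written: 100 per arm (200) where the rest of the paragraph implies 140 per arm (280). The 0.398 SD and GCSS 0.8 figures are arithmetically right for 100 completers per arm but are labelled as holding for enrolled patients. Under the accrual rule Aim 1 loses no power; even at exactly 280 enrolled and 30% dropout, 196 completers give 79.2% power at 0.398 SD.

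For visit completion, the caption's 100 per arm matches the survey-completer count and cannot be the denominator of that outcome. The stated 18.6 points is right for that N with continuity correction, and it is conservative for any realistic scheduled set. With at least 159 scheduled per arm, it falls to about 14.3 to 14.9 points or less. That range rests on the plan's 63% control attendance, equal arms, and an assumed N, because the documents state none. A reader should not conclude that any primary outcome is underpowered; the documents show a misstated size and an unstated denominator.

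**What to change.** In the sample-size paragraph of Section 4.a:

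1. Change the parenthesis after the 280 to 140 enrolled per arm.
2. Open the 0.398 SD sentence with 200 participants with complete responses (100 per arm) in place of 200 patients enrolled.
3. In the GCSS example, change enrolled to participants with complete responses.

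In Table 1:

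4. Label the caption's 100 per arm as participants with complete responses, applying to the survey outcomes.
5. Give the visit-completion row its own denominator, scheduled patients by randomised arm, with the expected N and the detectable difference that follows from it.

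Items 1 to 4 are wording only. Item 5 costs more than a restated row: it specifies the analysis population for a primary outcome. The sponsor must decide whether patients whom Section 4.a excludes after scheduling (those who switch modality, cannot be reached, decline, or miss a survey) are counted, and must supply an expected number scheduled. The design and the accrual rule stay as they are.
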